HRPO Protocol

1) Protocol Title (Version # and/or Version Date)

The Emotions and Decisions of Couples, #12-433, v. 06/13/2018

2) IRB Review History

N/A

3) Objectives

The proposed study is an experimental comparison of the effects of alcohol on arousal and emotion-regulation between 112 Distressed Violent (DV) and 112 Distressed Nonviolent (DNV) partners. One partner from each DV couple will be pseudo-randomly selected and yoked to a DNV partner of the same sex and a relationship satisfaction within a five-point range for participation in the experiment. To test the overall hypothesis that over-arousal is a mechanism through which alcohol is associated with increases in the frequency and severity of IPV, the selected partners will participate in a counter-balanced placebo session and alcohol administration session during which EEG, psychophysiology and pupillary response measurements of arousal will be collected during an emotion regulation task.

Specific Aim 1: To determine if normal increases in arousal after alcohol exposure is potentiated by evocative partner stimuli is greater for distressed violent (DV) partners compared to distressed nonviolent (DNV) partners. *Hypothesis 1a:* DV and DNV partners will experience comparable alcohol related increases in arousal. *Hypothesis 1b:* DV partners will demonstrate greater arousal increases by evocative partner displays than DNV partners. *Hypothesis 1c:* DV partners will experience greater arousal when exposed to alcohol and evocative partner stimuli than DNV partners.

Specific Aim 2: To determine if alcohol induced arousal interferes with DV partners' ability to regulate emotion in response to evocative partner stimuli compared to DNV partners. *Hypothesis 2a:* Emotion regulation during evocative stimuli will be reduced compared to neutral stimuli. *Hypothesis 2b:* Emotion regulation during evocative stimuli will be reduced by alcohol. *Hypothesis 2c:* DV partners will be less able to regulate emotion during evocative stimuli than DNV partners. *Hypothesis 2d:* Alcohol will interfere with DV partners' ability to regulate emotion during evocative stimuli compared to DNV partners.

4) Background

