Specific Aim 1: To determine if normal increases in arousal after alcohol exposure is potentiated by evocative partner stimuli and is greater for DV partners compared to DNV partners. We will conduct a 2 (beverage condition: alcohol vs. placebo) x 2 (stimulus: evocative vs. neutral) repeated measures ANOVA with a between-subjects factor (partner type: DV vs. DNV). To test whether alcohol increases overall arousal (**Hypothesis 1a**), we will examine the main effect of alcohol vs. placebo on arousal variables, collapsing across partners and stimuli during the WATCH condition as alcohol should effect the arousal of both partner types equally. To test whether DV partners are more aroused by evocative partner displays than DNV partners (**Hypothesis 1b**), we will test the interaction effect of partner type and stimulus type, collapsing across alcohol and placebo conditions. Finally, to test the hypothesis that alcohol induced increases in arousal above placebo will be greater for evocative than neutral stimuli (**Hypothesis 1c**) for DV vs. DNV partners, we will test the three-way interaction in the 2 (DV vs. DNV) x 2 (alcohol vs. placebo) x 2 (evocative vs. neutral) repeated measures ANOVA. Specifically, this contrast will examine the effect of partner type when comparing stimuli type (evocative) to beverage condition (alcohol) on arousal and provides a critical control given that conflict intensity may differ between DV and DNV couples. The 3-way interaction (Hyp1c) will allow us to be able to determine whether the change in arousal between alcohol and placebo sessions for the evocative stimuli differs between couple types. The arousal level of evocative stimuli is matched between alcohol and placebo sessions, thus allowing for a controlled examination of alcohol-induced increases in arousal for evocative stimuli across DV and DNV couples.

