Specific Aim 2: To determine if alcohol induced arousal interferes with DV partners' ability to regulate emotion in response to evocative partner stimuli compared to DNV partners. All hypotheses will be tested using a 2 (beverage condition: alcohol vs. placebo) x 2 (stimulus: evocative vs. neutral) x 2 (regulation condition: WATCH vs. DON'T REACT) repeated measures ANOVA with a between-subjects factor (partner type: DV vs. DNV). Testing specific interactions within the overall model will test each hypothesis. If the ages of the DV and DNV partners are significantly different, ANCOVAs will be conducted as age may further moderate the relationships tested in Aim 2. To test the hypothesis that emotional regulation during evocative partner stimuli will be reduced compared to regulation during neutral stimuli (**Hypothesis 2a**), we will test the 2 (evocative vs. neutral) x 2 (WATCH vs. DON'T REACT) interaction term, collapsing across partner type in the placebo condition. To test the hypothesis

that emotion regulation during evocative partner stimuli will be reduced by alcohol, (**Hypothesis 2b**) we will test the 2 (evocative vs. neutral) x 2 (WATCH vs. DON'T REACT) interaction term collapsing across partner type in the alcohol condition. To test the hypothesis that DV partners are less able to regulate emotion during evocative stimuli than the DNV partners (**Hypothesis 2c**), we will test the 2 (DV vs. DNV) x 2 (evocative vs. neutral) x 2 (WATCH vs. DON'T REACT) in the placebo condition. Finally, to test the hypothesis that alcohol interferes with the ability to regulate emotion for DV partners compared to DNV partners (**Hypothesis 2d**), we will test the 2 (DV vs. DNV) x 2 (alcohol vs. placebo) x 2 (evocative vs. neutral) x 2 (WATCH vs. DON'T REACT) interaction.

15) **Provisions to Monitor the Data to Ensure the Safety of Subjects**

1. The experienced and qualified professionals responsible for determining serious adverse events in the proposed study “Emotions and Decisions of Couples” will be the PI and co-Investigator for the study [name]. and [name]. [name] has experience with both oral and intravenous alcohol administration and will work with [name] to identify any adverse events.

Any serious adverse events that do occur during the course of the study will immediately be reported to the University of New Mexico Human Research Protections Office as an adverse event.

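### Age adjustment is absent from Aim 1, depends on a significance test in Aim 2, and does not specify how age enters the ANCOVA

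*Combined protocol and SAP*

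**What the plan says.** Section 3 (Objectives) describes a comparison "between 112 Distressed Violent (DV) and 112 Distressed Nonviolent (DNV) partners". Each DV partner is yoked to a DNV partner of the same sex with satisfaction within five points. Age is not a matching variable, and section 5 admits ages 21 to 45.

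The analysis plan is in section 14 (Data Management, Data Analysis Plan).

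- **Aim 1.** "We will conduct a 2 (beverage condition: alcohol vs. placebo) x 2 (stimulus: evocative vs. neutral) repeated measures ANOVA", with partner type between subjects. Hypothesis 1b is the partner type x stimulus interaction. For 1c, "we will test the three-way interaction in the 2 (DV vs. DNV) x 2 (alcohol vs. placebo) x 2 (evocative vs. neutral) repeated measures ANOVA". No age term or ANCOVA is mentioned.
- **Aim 2.** The model adds the regulation condition and is again a "repeated measures ANOVA with a between-subjects factor (partner type: DV vs. DNV"). "Testing specific interactions within the overall model will test each hypothesis". Hypothesis 2c is a three-way interaction with partner type in the placebo condition, and 2d is the four-way interaction. The age provision is here: "If the ages of the DV and DNV partners are significantly different, ANCOVAs will be conducted as age may further moderate" the relationships in this aim. The reason given is thus possible moderation by age.

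The plan gives no alpha for the age test. It does not say whether age would be a main effect only, crossed with the within-subject factors, or crossed with partner type, nor whether it would be centred.

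**The concern.** Membership of DV or DNV is not randomised, so a difference in age can produce or hide a difference between the groups in any contrast that varies with age. Three features of the plan leave this open.

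1. Hypotheses 1b and 1c compare the same two groups as 2c and 2d but are never adjusted, even if the age test is significant. No reason is given for treating the aims differently.
2. In Aim 2 the decision rests on a p-value for age. Confounding depends on the size of the gap and on how strongly age relates to the contrast. Moderation, the stated reason, does not depend on a mean difference at all.
3. The form of the ANCOVA is left open, and the forms do different things to the tested interactions.

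Hypotheses 1a, 2a and 2b collapse across partner type, so an age imbalance between the groups does not confound them.

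**Working it through.** The documents contain no power calculation, effect size or alpha to reproduce. The only numerical input from them is 112 per group. Two-sided 0.05, the age gap d (in SD units) and the correlation r between age and a subject's contrast score are assumptions.

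**1. What the trigger detects.** The smallest observed gap reaching significance is t(0.975, 222) x sqrt(2/112) = 1.971 x 0.1336 = 0.263 SD. The power of the age test, by normal approximation, is 0.32 at a true gap of 0.2 SD, 0.46 at 0.25 SD and 0.61 at 0.3 SD. A true 0.25 SD gap would therefore go unadjusted in about 54% of studies.

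**2. Type I error with no age term (1b and 1c as planned).** Each hypothesis with a partner-type term reduces to a two-group comparison of one contrast score per subject. If there is no true group effect and the score correlates r with age, the groups differ by r x d SD. The test is then shifted by λ = r x d x sqrt(112/2) = 7.483 x r x d, and the type I error is Φ(λ - 1.96) + Φ(-λ - 1.96).

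| r | λ at d = 0.25 | Type I error |
|---|---|---|
| 0.1 | 0.187 | 5.4% |
| 0.2 | 0.374 | 6.6% |
| 0.3 | 0.561 | 8.7% |
| 0.5 | 0.935 | 15.5% |

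Simulation agrees: about 9% at r = 0.3 and 15 to 16% at r = 0.5. At d = 0.1 and r = 0.3 the rate is 5.6%. At d = 0.5 the formula gives 20% (r = 0.3) and 46% (r = 0.5). A gap that large would be significant in about 96% of studies, and Aim 1 would still not be adjusted.

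**3. The conditional rule.** In 4,000 simulations per scenario (gaps of 0 to 0.5 SD, r of 0.3 or 0.5), the rule of adjusting only if age is significant, with age crossed with the within-subject factors, gave 4.6 to 5.9%. Always adjusting gave 4.4 to 5.7%. Other runs at gaps of 0.2 to 0.3 SD also stayed within about 5 to 6.5%. The worst conditional figure was 12.4%, among studies in which a 0.5 SD gap was missed at r = 0.5, and those were about 4% of studies.

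**4. What each form of ANCOVA does.** One data set was simulated with the full Aim 2 structure: 112 per group, a 0.5 SD age gap, a true age effect on the four-way contrast and no group effect. The partner type x beverage x stimulus x regulation coefficient was:

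- no age term: -0.0248 (SE 0.0340)
- age as a main effect only: -0.0248 (SE 0.0340), identical
- age crossed with the within-subject factors: -0.0757 (SE 0.0345)

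In complete data a main effect of age alters only the between-subject part of the model, so the tested term cannot move. Crossing age with the within-subject factors does change it. This is a single data set, so the direction and p-value of the change carry no meaning. None of these models contains age x partner type x contrast, the term that would test moderation of 2c or 2d by age.

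**The case against.** The strongest reply is that the design already removes most of what age could do. Beverage, stimulus and regulation vary within subjects, so an age effect on overall arousal or rating level cancels out of every tested contrast. Only an age effect on the contrast itself can confound, and the documents give no evidence of one. The age range is restricted. The inflation above depends on assumed correlations and is slight at 0.1 to 0.2. The authors also tie age to Aim 2 specifically, which may be a deliberate judgement. Age is only one of many ways in which unrandomised groups can differ, so adjusting for it removes only part of the confounding. All of this is fair and limits the size of the problem, but none of it explains why 1b and 1c are treated differently from 2c and 2d.

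Two stronger readings are tempting and are not supported. A reader might infer that the planned ANCOVA cannot correct the Aim 2 interactions at all. The plan does not say that age enters as a main effect only, and a repeated-measures ANCOVA commonly crosses a between-subject covariate with the within-subject factors, which does adjust 2c and 2d. A reader might also infer that the significance pre-test does serious damage by itself. With age properly crossed, the simulations put the cost at about one percentage point or little more.

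**Conclusion.** The concern holds for 1b, 1c, 2c and 2d. Its main part is the missing age adjustment in Aim 1. At an assumed 0.25 SD gap, the false-positive rate there is close to nominal if age correlates 0.1 to 0.2 with the contrast, and about 9% to 15-16% if it correlates 0.3 to 0.5. These are illustrations, since the documents supply neither the gap nor the correlation.

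In Aim 2 the trigger is poorly matched to its purpose but does little harm if age is crossed with the within-subject factors. If age enters as a main effect only, 2c and 2d are in effect unadjusted and the Aim 1 figures apply to them too. Neither form tests the age x partner type moderation of 2c and 2d that the stated reason implies. This is a gap in specification that should be closed before the data are analysed. It does not show that the planned comparisons are invalid.

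**What to change.** Remove the significance test on age. In the models for both aims, include age centred at the overall mean, with its interactions with the within-subject factors in each tested contrast, whatever the observed age difference. Centring keeps 1a, 2a and 2b interpretable at the average age and not at age zero. If moderation by age is of interest, add age x partner type x contrast as a separate, labelled secondary test.

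The cost is plan wording. Age is already established at screening for eligibility. For each between-group contrast, the age term takes residual degrees of freedom from 222 to 221, and the optional moderation term takes them to 220.

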Stimuli Acquisition: Video cameras will be focused on the face of each partner to capture the content of the partner's speech as well as the partner's facial expressions during the discussion of a disagreement using two Canon VIXIA HF R400 video cameras. To ensure that there are not experimenter-introduced differences in the evocative stimuli used between groups in the subsequent experimental sessions, and to ensure we choose sufficiently arousing partner displays, stimuli selected will be according to the hierarchy of the Specific Affect (SPAFF) coding system (e.g., contempt, belligerence, criticism, defensiveness, stonewalling, respectively). It is important to note that conflict intensity differences likely naturally exist between DV couples and DNV couples (see Significance). Our method will ensure, however, that there are no experimenter introduced differences in the stimuli selected. Inter-rater reliabilities will be calculated on 50% of the videos and coders retrained to criterion if necessary. DV couples display at least 192 evocative behaviors per 15-minute disagreement discussion,⁶⁷ and partners are roughly equivalent in such displays¹⁸ ensuring ample evocative stimuli for subsequent sessions. Displays of these evocative behaviors also distinguish DNV from satisfied couples.⁴⁰ Partners will be excluded from the remainder of the study should the couple fail to provide sufficient stimuli. If the couple is symmetrical in violent behavior, one partner will be randomly selected to participate in the remaining sessions. If the couple is asymmetrical, the most violent partner will be selected for participation. DV partners will be matched and yoked to a DNV partner of comparable distress.

Emotion-Regulation Sessions: The selected partners (DV, DNV) will return to the laboratory on two separate occasions for the completion of the emotion-regulation sessions of the study. Once participants are prepped for biopotential recording, they will be administered either an alcohol beverage or placebo beverage (counter-balanced alcohol and placebo conditions; see below for procedures).

Alcohol Condition Protocol - Participants will receive a mixed drink (juice and 100-proof vodka) intended to raise their blood alcohol concentration (BAC) to a target dose of 0.08g% using a standard formula for calibrating the alcohol doses to achieve the target BACs.⁶⁸

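### Hypothesis 2b claims that alcohol reduces emotion regulation, but its named test uses the alcohol session alone and so cannot show an alcohol effect in either direction

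*Combined protocol and SAP*

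**What the plan says.** Section 3 (Objectives) states Hypothesis 2b as "Emotion regulation during evocative stimuli will be reduced by alcohol". Section 14 (Data Analysis Plan, Specific Aim 2) repeats the claim.

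For the analysis, Section 14 first sets out a model with beverage as a factor: "All hypotheses will be tested using a 2 (beverage condition: alcohol vs. placebo" and so on, crossed with stimulus and regulation, with partner type between subjects. It adds: "Testing specific interactions within the overall model will test each hypothesis". It then names a term for each hypothesis:

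- **H2a:** the stimulus (evocative, neutral) by regulation (WATCH, DON'T REACT) "interaction term, collapsing across partner type in the placebo condition".
- **H2b:** the same two-factor "interaction term collapsing across partner type in the alcohol condition".
- **H2c:** partner type by stimulus by regulation, placebo session only.
- **H2d:** the four-way term, beginning "we will test the 2 (DV vs. DNV) x 2 (alcohol vs. placebo".

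Aim 1 is handled differently. For H1a, "we will examine the main effect of alcohol vs. placebo on arousal variables" is written out.

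**The concern.** A reduction caused by alcohol is a difference between the alcohol and placebo sessions. The term assigned to H2b contains no such difference. It asks H2a's question again in the other session: does regulation differ between evocative and neutral clips?

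H2a itself predicts a non-zero stimulus-by-regulation contrast under placebo. If H2a is true and alcohol does nothing, the same contrast is present in the alcohol session and the H2b test tends to be significant. Conversely, if alcohol abolishes regulation, the contrast under alcohol can be near zero and the test finds nothing.

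H2b is the only Aim 2 hypothesis about an overall alcohol effect on regulation. H2a and H2c use placebo only. H2d asks whether the alcohol effect differs between DV and DNV partners, and is null if alcohol impairs both groups equally.

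**Working it through.** **Set-up.** Let E and N be the mean WATCH minus DON'T REACT difference on evocative and neutral clips, with subscripts A (alcohol) and P (placebo).

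- H2a test as named: E_P − N_P = 0.
- H2b test as named: E_A − N_A = 0.
- What H2b claims: E is smaller in size under alcohol, so the matching contrast is E_A − E_P (beverage by regulation within evocative clips).
- Three-way beverage by stimulus by regulation: (E_A − N_A) − (E_P − N_P).

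The plan gives no power figure for this hypothesis, so there is none to reproduce.

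**Inputs.** n = 112 + 112 = 224 selected partners (Sections 3 and 6). Everything else is assumed: two-sided 0.05, no dropout, each regulation effect with SD 1, within-session correlation 0.5 (so E − N has variance 1 + 1 − 2 × 0.5 = 1), and between-session correlation 0.3 unless stated.

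**Step 1: no alcohol effect.** The named test is a one-sample t test with noncentrality dz × √224 = 14.967 × dz.

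| dz of E − N, same in both sessions | Noncentrality | Named H2b test rejects |
|---|---|---|
| 0 | 0 | 0.050 |
| 0.05 | 0.748 | 0.116 |
| 0.1 | 1.497 | 0.320 |
| 0.2 | 2.993 | 0.846 |
| 0.3 | 4.490 | 0.994 |

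A contrast that includes beverage rejects about 0.05 throughout.

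**Step 2: all three tests by simulation** (20,000 replicates). Effects are written evocative/neutral.

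| Placebo → alcohol | Named test | Three-way | Beverage × regulation, evocative |
|---|---|---|---|
| 0.3/0.6, no change | 0.994 | 0.051 | 0.050 |
| 0.3/0, no change | 0.994 | 0.051 | 0.051 |
| 0.3/0.6 → 0/0.3 (equal drop) | 0.995 | 0.048 | 0.965 |
| 0.3/0.6 → 0/0.6 (evocative lost) | 1.000 | 0.968 | 0.967 |
| 0.3/0 → 0/0 (evocative lost) | 0.050 | 0.968 | 0.968 |
| 0.3/0.6 → 0/0 (both lost) | 0.050 | 0.966 | 0.965 |
| 0.5/0.5 → 0.2/0.2 (equal drop) | 0.053 | 0.054 | 0.965 |

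The last five rows all have the same evocative loss of 0.3 SD. The named test ranges from 5% to 100% across them, depending only on the neutral clips.

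Hand check of the last column: the SD of a between-session difference is √(2 × (1 − 0.3)) = 1.183; 0.3/1.183 × 14.967 = 3.795; Φ(3.795 − 1.96) = 0.967.

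With between-session correlation from 0 to 0.7 (10,000 replicates), in the 0.3/0 and 0.5/0.5 loss cases the named test stays at 0.047 to 0.053. The evocative contrast gives 0.887 to 1.000.

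**Step 3: reading H2a beside H2b.** Probability that exactly one of the two is significant when alcohol does nothing:

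| Between-session correlation | dz 0.1 | dz 0.2 | dz 0.3 |
|---|---|---|---|
| 0 | 0.433 | 0.261 | 0.011 |
| 0.3 | 0.360 | 0.220 | 0.012 |
| 0.7 | 0.225 | 0.148 | 0.009 |

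Check at correlation 0 and dz 0.2: 2 × 0.846 × 0.154 = 0.261. The informal comparison fails the other way too. If the contrast falls from 0.5 to 0.3, both tests are significant in 99% or more of runs, and the same holds if it rises from 0.3 to 0.5.

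**The case against.** **Beverage is in the overall model.** A stimulus-by-regulation term at one level of beverage is a legitimate simple interaction within that model, and H2a and H2c are built the same way. That is fair. The general sentences and the H2b term sit awkwardly together, but the fault is better described as a mismatch between hypothesis and contrast than as a flat contradiction. It does not rescue H2b: H2a and H2c make no claim about alcohol, so placebo-only terms suit them, whereas H2b does make one.

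**One missed-effect case has another cause.** When both clip types start equal and drop equally, the three-way interaction also misses (0.054). That miss comes from measuring regulation as evocative minus neutral, so adding beverage to the existing term would not cure it. This stands, and it bears on which fix to choose.

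**The smallest repair is the three-way interaction.** It keeps neutral clips as the control, as the plan does throughout Aim 2. This is a reasonable alternative reading. The hypothesis, however, concerns regulation during evocative clips and makes no claim that the loss is confined to them, so the evocative-clip contrast fits it more closely.

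**The figures are illustrative.** The 97% rests on an assumed 0.3 SD loss and correlation 0.3. The 85% and 99% need a contrast of 0.2 to 0.3. Exclusions after enrolment (pregnancy, positive UA, insufficient stimuli) would bring n below 224. All true; the percentages would move, but the absence of a placebo comparison would not.

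**H2d carries Aim 2 and does compare beverages.** Correct, and it limits the consequence to H2b. The data are collected either way, so nothing is lost if the wording is corrected before analysis.

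**Conclusion.** The concern holds. The term named for H2b does not test H2b, and no other planned test supplies the missing overall alcohol-versus-placebo comparison of regulation. Followed as written, the plan could declare H2b supported when alcohol does nothing (12% to 99% of the time for contrasts of 0.05 to 0.3 SD). It could also declare H2b unsupported when a 0.3 SD loss on evocative clips is real: about 5% rejection in three of the five loss scenarios, against about 97% for the matching contrast.

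These sizes rest on assumed alpha, effect sizes and correlations, and on n = 224 with no dropout. The conclusion that the test and the hypothesis do not match rests on the text alone. H1a, H1c and H2d do compare alcohol with placebo and are unaffected. The point must be fixed, because a named hypothesis otherwise has no valid test.

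**What to change.** Replace the H2b sentence in Section 14, before any results are seen, with wording to this effect:

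> H2b will be tested by the beverage (alcohol, placebo) by regulation (WATCH, DON'T REACT) contrast within evocative clips, averaged over partner type. H2b is supported if the WATCH minus DON'T REACT difference is smaller in size in the alcohol session. The beverage by stimulus by regulation interaction will be reported alongside, to show whether any reduction is specific to evocative clips.

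The three-way interaction should not act as a gate, because it is zero when alcohol lowers regulation equally for both clip types. It is still needed beside the main test, because the evocative-clip contrast alone cannot show specificity.

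The cost is this change of wording. Section 11 (Emotion-Regulation Sessions) says that selected partners "will return to the laboratory on two separate occasions for the completion of the emotion-regulation sessions", so the paired data already exist by design. Both contrasts can be estimated from the planned model.
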